10.2.3. Period 3: Open-label Treatment

After 24 hours of the initial start of study drug, subjects with a reduction in average GIR <20% at 24 hours will be assigned to open-label CSI-Glucagon™.

After 48 hours of the initial start of study drug, subjects with a reduction in average GIR $\geq 20\%$ at 24 hours will be assigned to open-label CSI-Glucagon™.

After a subject is assigned to open-label CSI-Glucagon™, the following procedures will be performed.

Note: If continuous enteric feed was reduced in period 2 and increased feeding is necessary by the algorithm, the same rate as established during period 1 should be the target, and any additional demands will be covered with the IV GIR.

Period 3:

At the start of open-label treatment:

1. Photograph the site of approximate cannula insertion prior to application of a new OmniPod® pump.
2. Using the same procedures for loading and weighing the pump, and confirming cannula deployment as detailed for Day 0, apply a new OmniPod® pump containing CSI-

Glucagon™ (5 mg/mL), instruct the pump to insert the cannula and set basal rate of 5 µg/kg/hr. Record time of starting the pump; this is t=0.

3. Adjust IV fluids as per the Day 1 procedures.
4. At 4 hours, remove the OmniPod® pump and:
 - a. Photograph the application site, paying particular attention to the cannula insertion site.
 - b. Assess site for edema and erythema using the Draize scale. Any Draize scores > 0 should be followed to resolution, including a follow-up photograph.
5. The investigator should provide an assessment as to whether continued treatment would be helpful for clinical care.
 - a. If yes, and open-label treatment will be continuing, perform “real-world” pump change-out procedure (see Section 9.3.3).
 - b. If no, and open label treatment is ending, remove CGM and draw blood for immunogenicity testing, plasma insulin and glucagon levels as well as CBC, and CMP. Do not perform the “real-world” pump change-out procedure in this case.
6. If CSI-Glucagon™ treatment is considered helpful for clinical care, therapy may continue, including intermittently should procedures, e.g., PET scan, require temporary discontinuation, for up to a cumulative 28-day glucagon exposure.
 - a. Using the same procedures for loading and weighing the pump, and confirming cannula deployment as detailed for Day 0, a new OmniPod® pump containing CSI-Glucagon™ solution should be placed immediately and again at least every 72 hours, including any time the pump alarms due to an occlusion.
 - b. Each time a pump is replaced, the safety of pump switch out procedures should be as assessed by occurrence of blood glucose < 50 mg/dL.
 - c. Each time a pump is removed, including at final termination of therapy, the pump should be weighed, and the placement site should be photographed and assessed with Draize scales and any reactions followed to resolution.
 - d. POC glucose will be assessed every three hours; or more frequently if the CGM shows glucose falling <70 mg/dL (3.9 mmol/L) or rising above >200 mg/dL (11.1 mmol/L). Additionally, the trajectory of change in plasma glucose concentration based on the two most recent POC measurements should be used to adjust the frequency of glucose monitoring as needed to prevent plasma glucose <70 mg/dL (3.9 mmol/L) or >200 mg/dL (11.1 mmol/L).
 - e. CGM will be utilized for rapid alerts, which will trigger POC assessments of blood glucose that will be used to guide clinical decisions. At least 2 hours prior to each planned pump change, confirm the CGM sensor is working and place another as needed.
 - f. Every 2 weeks during treatment, draw blood for immunogenicity testing.
7. Whenever CSI-Glucagon™ treatment is temporarily paused and when treatment ends:
 - a. Draw blood for CBC, CMP, immunogenicity testing and plasma insulin and glucagon.
 - b. Perform physical exam and measure height and weight.

- c. Resume IV fluids at pre-study rate and manage glucose as per standard procedures.

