6.4. Clinical Experience with Glucagon

6.4.1. Clinical Experience with Approved Glucagon Products

Glucagon has a long history of medical use in the US, and is currently marketed by Eli Lilly & Co. as Glucagon for Injection [rDNA origin], and Novo Nordisk as GlucaGen® HypoKit®, both RLDs for treatment of severe hypoglycemia. Glucagon has a rapid onset of action and an extremely short half-life, and its safety, efficacy and clinical pharmacology have been well established. Prior to the current recombinant products, animal-sourced glucagon was marketed. The Agency first approved glucagon for use in humans in 1960.

Of relevance to the proposed indication in infants up to 1 year of age, animal derived glucagon was delivered via IM and IV routes to neonates at doses up to 100 µg/kg with no apparent adverse effects [9].

Published information on the safety, efficacy, immunogenicity and post-marketing surveillance of Lilly glucagon as rescue therapy for severe hypoglycemia is referenced to Xeris' current [Investigator's Brochure](#).

6.4.2. Clinical Experience with Approved Glucagon Products used Off-label to Treat Congenital Hyperinsulinism

Mohnike et al. reported a retrospective review of nine (9) CHI patient cases where continuous subcutaneous (SC) glucagon (reconstituted Novo GlucaGen®) was used as a treatment option (1 - 3 mg/day), with or without concomitant octreotide [5]. The objectives of using continuous SC glucagon were to:

- Stabilize blood glucose levels for several weeks without the use of high-volume dextrose infusions administered via a central catheter, which often causes bloating, and
- Avoid pancreatectomy or resurgeries (further reduction of pancreatic tissue) in patients with diffuse CHI.

The clinical outcomes of using continuous SC glucagon to treat CHI patients in this retrospective review were reported as follows:

- Central glucose infusions were reduced significantly or eliminated in all 9 children;
- SC glucagon was continued in 3 children for 1-4 years without further symptomatic hypoglycemia, convulsions or unconsciousness;
- Glucagon treatment was initiated to manage recurrent hypoglycemia after subtotal pancreatectomy in 2 of 9 children;
- Pancreatectomy or subsequent resurgeries (to remove additional pancreatic tissue and further reduce insulin output) were avoided in 5 of the 9 children;

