 - b. If GIR cannot be reduced because glucose level is < 70 mg/dL (3.9 mmol/L), **restore continuous enteric feeding if that has been suspended**, or increase glucose infusion rate by 2 mg/kg/min and **increase study drug infusion rate by 5 µg/kg/hour (to a maximum of 20 µg/kg/hr)** and check blood glucose in 1 hour.
 10. If glucose is <50 mg/dL (2.8 mmol/L), give 200 mg/kg dextrose by IV push, increase GIR by 2 mg/kg/min, **increase study drug infusion rate by 5 µg/kg/hour (to a maximum of 20 µg/kg/hr)** and check blood glucose in 30 minutes. At 12 hours after start of study drug, determine average GIR since the start of blinded therapy, excluding the first 2 hours. If average “on treatment” GIR has been reduced by < 20% from the baseline value determined in Period 1, take the following actions:
 - a. Remove the pump and weigh it.
 - b. Replace the pump with a new one at the same flow rate setting as the previous pump and a fresh supply of the same blinded study drug.
 - c. Monitor POC glucose over the next 12 hours, adjusting GIR using the same rules as above for making IV fluid adjustments in the interim.

{Note: This same procedure should be followed if the pump alarms or if there is an acute deterioration in an otherwise stable subject, indicating a possible occlusion.}

Day 1

At 24 hours after the initial start of study drug, determine average GIR since the start of blinded therapy, excluding the first 2 hours. Then compare the “on treatment” GIR to the baseline value determined in Period 1 and calculate the percentage change. Depending on percentage change in GIR, follow the procedures under either item 1 or item 2.

1. At 24 hours if average GIR has been reduced by < 20% from the baseline value determined in Period 1, complete the following procedures:

- a. Draw blood for plasma insulin and glucagon levels as well as CBC and CMP.
 - b. Remove and weigh the OmniPod® pump (Appendix 2) and:
 - a. Photograph the application site, paying particular attention to the cannula insertion site.
 - o Assess site for edema and erythema using the Draize scale. Any Draize scores >0 should be followed to resolution, including a follow-up photograph.
 - c. Proceed to Period 3 (see 10.2.3).
2. At 24 hours if average GIR has been reduced by $\geq 20\%$ from the baseline value determined in Period 1, complete the following procedures:
- a. Continue to adjust the GIR during day 1 as per day 0.

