If GIR=0, continuous enteric feeding has been completely weaned, and plasma glucose continues to rise, reduce study drug infusion rate by 2.5 $\mu\text{g}/\text{kg}/\text{hr}$ every 6 hours to a minimum of 2.5 $\mu\text{g}/\text{kg}/\text{hr}$, as long as the pre-meal blood glucose is >70 mg/dL (3.9 mmol/L).

At approximately 48 hours from the start of the first blinded study treatment, complete the following:
 - b. Draw blood for insulin and glucagon levels as well as CBC and CMP.
 - c. Remove the OmniPod® pump, weigh it, and photograph the application site, paying particular attention to the cannula insertion site.
 - d. Assess site for edema and erythema using the Draize scale. Any Draize scores > 0 should be followed to resolution, including a follow-up photograph.
 - e. Proceed to Period 3 (see 10.2.3).

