13.2.3. Pharmacokinetics

Pharmacokinetic (PK) data of steady state glucagon concentrations following continuous subcutaneous infusion will be analyzed descriptively.

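### In Period 3 the glucagon sample at a 4-hour stop is drawn after pump removal and later draws are untimed, so infants randomized to placebo have no guaranteed on-infusion level of active drug

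*Combined protocol and SAP*

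**What the plan says.** **Period 3, stop at 4 hours.** Section 10.2.3 step 4 reads "At 4 hours, remove the OmniPod® pump and", and goes on to the photograph and Draize score. Step 5 then asks the investigator whether continuing would help. If not, step 5b applies: "If no, and open label treatment is ending, remove CGM and draw blood for immunogenicity testing, plasma insulin and glucagon levels". The Synopsis, Period 3, follows the same sequence.

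**Period 3, later pause or end.** Step 7 opens "Whenever CSI-Glucagon™ treatment is temporarily paused and when treatment ends" and lists blood sampling (including glucagon and insulin), a physical examination and the return to IV fluids. It does not mention pump removal or give a time window. The Synopsis is equally open.

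**Period 2.** In Section 10.2.2, at 24 hours for non-responders, the draw is item a, "Draw blood for plasma insulin and glucagon levels as well as CBC and CMP", and pump removal is item b, "Remove and weigh the OmniPod® pump (Appendix 2) and". At 48 hours for responders, the draw, "Draw blood for insulin and glucagon levels as well as CBC and CMP", is again listed ahead of removal.

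**Purpose and half-life.** Section 13.2.3: "Pharmacokinetic (PK) data of steady state glucagon concentrations following continuous subcutaneous infusion will be analyzed descriptively". Section 6.4.1, on approved products: "Glucagon has a rapid onset of action and an extremely short half-life". No half-life figure is given.

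**Schedule.** Section 11.1 states 3 PK samples over the first 3 days. Table 4 marks plasma glucagon/insulin on Days 0, 1 and 2, with a dash under Q3D. Table 5 gives Day 0, then Day 1 for non-responders or Day 2 for responders, then a 2 mL PK sample at Period 3 pauses or end.

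**The concern.** A steady-state summary needs samples taken while the drug is running, or at least at a known time after it stops. Once the pump is off, the level falls at a rate the protocol describes only as fast, and the photograph, site score and continuation assessment all come between removal and the draw. Section 10.2.3 does not ask for the interval to be recorded.

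This matters most for infants randomized to placebo. Section 9.3.1 says the placebo contains no glucagon, so these infants first receive active drug in Period 3. For both arms, the pause/end draw is also the only exposure measurement in Section 10.2.3 during up to 28 days of cumulative use. If off-pump and on-pump levels were summarized together as steady state, exposure would be understated by an unknown amount.

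**Working it through.** **1. Reproduce the plan's own count.** Table 4 gives Day 0 + Day 1 + Day 2 = 1 + 1 + 1 = 3, which matches the 3 samples in Section 11.1. Section 10.2.2 with Table 5 gives Day 0 + (Day 1 or Day 2) = 1 + 1 = 2. On that schedule a third arises only if treatment pauses or ends within the first 3 days. The two schedules do not agree.

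**2. Place each sample against the pump**, using Section 10.2 and Table 5.

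| Sample | Randomized to glucagon | Randomized to placebo |
|---|---|---|
| Day 0 | before any study drug | before any study drug |
| 24 h or 48 h | on active infusion, before removal | on placebo |
| Period 3, stop at 4 h (step 5b) | after pump removal | after pump removal |
| Period 3, later pause or end (step 7) | order not stated | order not stated |
| Guaranteed on active infusion | at least 1, if Period 2 is completed | 0 |

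**3. Count the infants affected.** Section 13.1 plans 6 per arm at the interim analysis and 9 or 12 at the final one. Infants with no guaranteed on-infusion level of active drug are therefore 6 of 12, 9 of 18 or 12 of 24, which is 50% each time.

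**4. Check whether Table 4 closes the gap.** Its Day 2 mark sits under the Period 3 heading. Footnote f, which moves tests to Day 1 for infants switched at 24 hours, is attached to the CBC, CMP and pump-placement rows but not to the PK row. Read that way, a placebo infant switched at 24 hours and still treated on Day 2 would have a sample during open-label infusion. However, Table 5 assigns the Day 2 PK sample to responders, as part of Period 2, and Section 10.2.3 has no matching step. The mark may help some infants, but the documents do not settle it.

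**5. Illustrate the size, by assumption only.** With first-order decline, the share of the on-infusion level left is 0.5^(delay / half-life). Both inputs are assumed.

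| Assumed effective half-life | 5 min after removal | 15 min | 30 min |
|---|---|---|---|
| 5 min | 50% | 13% | 2% |
| 10 min | 71% | 35% | 13% |
| 20 min | 84% | 59% | 35% |
| 40 min | 92% | 77% | 59% |

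For example, 0.5^(15/20) = 0.59. The calculation ignores the infant's own glucagon, which sets a floor, and any subcutaneous depot not captured by the effective half-life. It shows only that the answer runs from trivial to severe depending on two quantities the plan does not give.

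**The case against.** The strongest reply is that little depends on these samples. PK is not among the secondary objectives in Section 5.2, Section 13.2.3 is one descriptive sentence, and the primary endpoint and interim rule do not use it. The pre-removal samples at 24 and 48 hours can supply a steady-state summary for the glucagon arm. The pause/end draw is taken along with safety and immunogenicity blood, and no text says explicitly that it enters that summary. The half-life remark concerns approved products, not this formulation given by subcutaneous pump. Sampling procedures are to be supplied separately (Section 11), so draw times may be captured elsewhere.

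Most of this stands, and it limits the point to a minor one. It does not explain why Period 3 reverses the Period 2 order. Table 5 also puts the pause/end sample in its PK column without giving it an off-drug purpose.

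A reader might infer that every Period 3 sample is drawn after the pump has stopped. The documents do not support that: the order is explicit only for a stop at 4 hours, and a draw just before pump stop would comply with step 7. A reader might also infer that the Period 3 sample is the only on-drug level in most infants. That fails for the glucagon arm, and even in the placebo arm Table 4 may provide another for some.

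**Conclusion.** The point holds in a limited form. For infants who stop open-label treatment at 4 hours, the written sequence produces an off-infusion level that does not fit the stated steady-state aim. For later pauses and the end of treatment, the fault is silence about timing rather than a wrong order. The consequence falls on the placebo arm: 6, 9 or 12 infants without a guaranteed on-infusion level of active drug under Section 10.2 and Table 5.

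These counts assume the planned arm sizes and that the Table 4 Day 2 mark is not relied on; if it is honoured, fewer infants are affected. The bias in measured concentration is unknown. The percentages above are illustrations and should not be cited as estimates. The efficacy conclusions are unaffected.

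**What to change.** - In Section 10.2.3 (steps 4, 5b and 7) and the matching Synopsis text, state that at a planned stop or pause the already scheduled glucagon/insulin sample is taken while the pump is still infusing, immediately before deactivation, as in Period 2.
- Record the draw time, the pump-stop time and the infusion rate at the draw. The rate matters because it can be adjusted during treatment and, under Section 7.2, dosing may be tapered in some circumstances.
- In Section 13.2.3, say that samples drawn after an unplanned stop are listed but left out of the steady-state summary.
- Reconcile the PK schedule across Table 4 (Day 2 mark and Q3D dash), Table 5, Section 11.1 and Section 10.2.

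The cost is a reordering and three recorded items, with no extra blood. With the draw moved at planned stops, every infant who reaches one would have at least one on-infusion level: 12 of 12, 18 of 18 or 24 of 24 if all do, against 6, 9 or 12 now guaranteed. The downside is that at 4 hours the continuation assessment is made just before pump removal instead of after it. Section 9.3.3 already points that way, because for infants who continue it places the new pump before the existing one is deactivated. The change concerns sampling only and leaves the treatment rules as they are.

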10.2.4. Period 4, Post-treatment Immunogenicity Testing

At 28±14 days after receiving the last dose of glucagon in the study, subjects should have blood drawn for immunogenicity testing. Preferably, this will be done at the study site. If travel or other considerations preclude the subject returning to the study site, the blood draw may be performed at a local hospital, laboratory or clinic, or by home health care professional. In this case, the plasma sample will be sent directly to the central lab for testing. Xeris or its designee will coordinate with the site and the subject to facilitate collection, processing and shipping of this blood sample.

10.3. Subject Withdrawal

Subjects may withdraw from the study at any time at the parent/guardian's request or they may be withdrawn any time at the discretion of the investigator or sponsor, for safety, behavioral or administrative reasons. In any circumstance, every effort should be made to document the subject's outcome, if possible. Information regarding the reason for not completing the study will be recorded on the appropriate case report forms. The investigator should inquire about the reason for withdrawal and follow-up with the subject regarding any unresolved AEs. It will be documented whether or not each subject completed the clinical study. Any subject who receives at least one treatment dose of study medication will be included in the safety analysis.

If a decision by the investigator or sponsor is made to withdraw a subject, a final examination should be scheduled soon after the decision to withdraw is made. The following assessments should be completed if possible at this examination:

- Update any changes to medical history and concomitant medications.
- Perform physical examination and measure height and weight.
- Collect blood pressure and pulse rate measurements.
- Obtain blood samples as outlined in Schedule of Activities

If the subject is withdrawn from the study and parent/guardian also withdraws consent, no further evaluations should be performed, and no additional data should be collected. The sponsor may retain and continue to use any data collected before such withdrawal of consent.

Table 4: Schedule of Assessments and Procedures

Assessment	Screening	Period 1: Baseline GIR	Period 2: Randomized treatment		Period 3: Open-Label Treatment		Period 4: Post- Treatment
		Day -1	Day 0	Day 1	Day 2	Q3D	
Informed consent	x	—	—	—	—	—	
Demographic data	x	—	—	—	—	—	
Medical history	x	—	—	—	—	—	
Concomitant medications	x	x ^a	x ^a	x ^a	x ^a	x ^a	
Review eligibility	x	—	—	—	—	—	
Physical exam & weight	x	—	—	—	—	x ^b	
Vital signs (CRM)	x	x	x	x	x	x	
Hematology (CBC)	x ^c	—	—	—	x ^f	x ^b	
Clinical chemistry (CMP)	x ^c	—	—	—	x ^f	x ^b	
Blood glucose (POC)	x	x	x	x	x	x	
Immunogenicity	—	—	x	—	—	x ^d	x ^g
Plasma glucagon/insulin	—	—	x	x	x	—	
Wean diazoxide and octreotide	—	x	—	—	—	—	
Adjust GIR (and continuous enteric feed) when GIR=0	—	x	x	x	x	x	
Insert new CGM sensor	—	—	x	—	—	x ^e	
Photograph planned insertion site; weigh & place new OmniPod®	—	—	x	—	x ^f	x	
Remove & weigh OmniPod®; photograph and assess site with Draize scales	—	—	—	x	@ 4 hrs	x	
Adverse events	—	—	x	x	x	x	

^a Update as applicable.

^b Complete only when treatment ends or pauses.

^c Normal clinical care samples drawn within 7 days of the intended start of Period 2 will satisfy this requirement.

^d To be drawn every 2 weeks during open-label treatment, Day 14 and 28 (if applicable), whenever treatment is paused, and at the end of open-label treatment.

^e Weekly or as needed.

^f Will be performed on Day 1 if subject is a treatment failure and is switched to open-label treatment at 24 hours.

^g To be drawn at 28 ±14 days post-glucagon treatment.

11. ASSESSMENTS

Every effort should be made to ensure that the protocol-required tests and procedures are completed as described. However, it is anticipated that from time to time there may be circumstances outside the control of the investigator who will take all steps necessary to ensure the safety and well-being of the subject. When a protocol-required test cannot be performed, the investigator will document the reason(s) and any corrective and preventive actions taken to ensure that study processes are adhered to as soon as possible. The study team and the Sponsor will be informed of these incidents in a timely fashion.

For all blood collections, every effort must be made to obtain these samples at the same clock time each day. Blood collections and other study procedures should be performed at the time periods specified in the Schedule of Activities. With the exception of blood samples for determination of plasma glucagon, and insulin concentrations and immunogenicity testing, all biological samples will be assayed at onsite clinical laboratories. Procedures for the proper processing, storage and shipment of samples to offsite laboratories will be provided to all investigators prior to the start of the study.

11.1. Blood Volume

There will be 3 PK blood samples of about 2.0 mL each drawn over the first 3 days of treatment, plus a 1 mL sample for immunogenicity testing at the start of treatment. Hematology and chemistry panels will be collected at Screening, at the end of blinded treatment and at the end of open-label treatment. Testing performed as part of routine care may be used to satisfy the Screening requirement for hematology and chemistry. The amount of blood drawn on any particular day for study-specific procedures will not exceed 5% of estimated blood volume based on the weight of the subject (Table 5). All subjects exposed to CSI-Glucagon™ will have additional 1 mL blood samples for immunogenicity testing collected at 14 and 28 days of open-label treatment (if applicable), whenever treatment is paused, at the end of open-label treatment, and again at 28 ±14 days following the last dose.

Table 5: Volume of Blood Collections for Study-Specific Testing

	Sample Type	Hematology	Chemistry	Immunogenicity*	PK (insulin and glucagon)**	Total (mL)
Volume/Day	Screen	1***	1***	-	-	2
	Period 2, Day 0	-	-	1	2	3
	Period 2, Day 1 non-responders	1	1	-	2	4
	Period 2, Day 2 responders	1	1	-	2	4
	Period 3, Day 14 (if applicable)	-	-	1	-	1
	Period 3, Day 28 (if applicable)	-	-	1	-	1
	Period 3 Pauses/End	1	1	1	2	5
	Post Treatment****	-	-	1	-	1

*Note: Testing will be repeated whenever CSI-Glucagon™ treatment is temporarily paused, when treatment ends and at 28±14 days following the last dose of CSI-Glucagon™.

**Note: POC glucose samples are not reflected in this table, given the small volume of blood that is needed (~1.2 µl/sample) for plasma glucose measurements at bedside.

*** If not performed within 7 days of the start of study treatment as part of routine clinical care.

****At 28±14 days after the study treatment ends.

